5.2.2. Relative Dose Intensity

Relative dose intensity (RDI) is the percentage of the total amount of study drug administered relative to the total amount of study drug expected to be administered during a patient's actual on-treatment period based on the study drug regimen.

For magrolimab:

The relative dose intensity is the percentage of the total amount of study drug administered relative to the total amount of study drug expected to be administered, and will be calculated for each cohort, respectively:

Relative dose intensity (%) =
$$\left(\frac{\text{Cumulative Dosage of Magrolimab Administered (in mg/kg)}}{\text{Magrolimab Dosage Expected to be Administered on Treatment (in mg/kg)}}\right) x 100$$

Cumulative dosage (mg/kg) received for each patient is defined as the sum of dosages (mg/kg) of all infusions the patient received from Day 1 and onward.

Magrolimab dosage expected to be administered on treatment (mg/kg) for each patient is defined as the product of the assigned dose of magrolimab and number of doses the patient was scheduled to receive during the treatment period from Day 1, and it will include number of infusions administered plus the number of infusions not administered.

For venetoclax:

Relative dose intensity (%) =
$$\left(\frac{\text{Total Amount of Venetoclax Administered (mg)}}{\text{Venetoclax Expected to be Administered on Treatment (mg)}}\right) \times 100$$

For azacitidine, mitoxantrone, etoposide and cytarabine, take azacitidine RDI for example:

Relative dose intensity (%) =
$$\left(\frac{\text{Total Amount of Azacitidine Administered (mg/m}^2)}{\text{Azacitidine Expected to be Administered on Treatment (mg/m}^2)}\right) \times 100$$

For each study drug, descriptive statistics for the relative dose intensity with the number and percentage of patients belonging to relative dose intensity categories (eg, < 75%, ≥ 75 to < 90%, $\ge 90\%$) will be provided by treatment group for the Safety Analysis Set.

5.2.2.1. On-Treatment Intensity Per Cycle

The level of on-treatment intensity per cycle will be determined by considering doses and durations of treatment cycle that a subject receives may vary between cycles or deviate from the planned 28-day cycle length. For each study drug venetoclax, azacitidine, mitoxantrone, etoposide and cytarabine, the actual cycle length of a cycle, except the last cycle of the treatment, is determined as the interval from Day 1 of the cycle to Day 1 of the subsequent cycle; the actual length of last cycle is determined by Day 1 of the last cycle, to the death date and last dosing date.

For azacitidine, mitoxantrone, etoposide and cytarabine:

$$On-Treatment\ Intensity\ per\ 28-day\ Cycle\ (\%) = \frac{Amount\ of\ Doses\ Administered\ within\ a\ Cycle\ (mg/m^2)}{Amount\ of\ Doses\ Specified\ by\ Protocol\ within\ the\ Cycle\ (mg/m^2)}\ x\ 100,$$

averaged across all cycles treated.

On-Treatment Intensity per Actual Cycle Duration (%) =

 $\frac{\text{Amount of Doses Administered within a Cycle (mg/m}^2) / \text{Actual Cycle Length}}{\text{Amount of Doses Specified by Protocol within the Cycle (mg/m}^2) / 28 \text{ Days}} \times 100,$

averaged across all cycles treated.

For venetoclax:

On-Treatment Intensity per 28-day Cycle (%)= (
$$\frac{\text{Number of Days on Venetoclax within a Cycle}}{28 \text{ Days}} \times 100$$
),

averaged across all cycles treated

On-Treatment Intensity per Actual Cycle Duration (%)
$$= (\frac{\text{Number of Days on Venetoclax within a Cycle}}{\text{Actual Cycle Length (Days)}} \times 100),$$

averaged across all cycles treated

Additionally, the average dosing of venetoclax per cycle will be calculated as:

Average Dosing per 28-day Cycle (mg)=
$$\frac{\sum \text{Dose of Venetoclax (mg)} \times \text{Number of Days on Venetoclax within a Cycle}}{28 \text{ Days}}$$

averaged across all cycles treated.

Average Dosing per Actual Cycle Duration (mg)=
$$\frac{\sum \text{Dose of Venetoclax (mg)} \times \text{Number of Days on Venetoclax within a Cycle}}{\text{Actual Cycle Length (Days)}}$$

averaged across all cycles treated.

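### SAP 5.2.2.1 does not settle which date closes the last cycle, so one intensity measure can far exceed 100% at full compliance; SAP 5.2.2 defines expected magrolimab in two conflicting ways

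*SAP*

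**What the plan says.** **Cycle length (SAP 5.2.2.1).** Cycles can "deviate from the planned 28-day cycle length", so the section defines an actual length for venetoclax, azacitidine, mitoxantrone, etoposide and cytarabine. For every cycle but the last, it "is determined as the interval from Day 1 of the cycle to Day 1 of the subsequent cycle". For the last cycle, "the actual length of last cycle is determined by Day 1 of the last cycle, to the death date and last dosing date". The per-actual-duration measure for azacitidine and the three MEC drugs divides the dose given by this length, and divides that by the protocol dose over 28 days. The result is "averaged across all cycles treated".

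**Expected magrolimab (SAP 5.2.2).** The section opens by defining relative dose intensity (RDI) for any study drug against the amount "expected to be administered during a patient's actual on-treatment period based on the study drug regimen". The magrolimab paragraph then makes the denominator "the product of the assigned dose of magrolimab and number of doses the patient was scheduled to receive". The numerator is "the sum of dosages (mg/kg) of all infusions the patient received from Day 1 and onward". Section 1.2 lists magrolimab at 1, 15 and 30 mg/kg in each cohort's regimen, and section 7.5 refers to repriming. RDI is reported in three categories: below 75%, 75% to below 90%, and 90% or more.

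**The concern.** A dose-intensity measure should return 100% for a patient who received exactly what was planned. Two rules here may not.

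- **Last cycle.** Earlier cycles include the drug-free days before the next Day 1; the last cycle does not. The sentence also joins two dates without saying whether the earlier, the later or only one of them applies, so it cannot be programmed without a guess. Numerator and reference rate then rest on different time bases.
- **Magrolimab.** If some infusions are scheduled at a lower level but all are charged at a single assigned dose, the denominator exceeds the planned amount.

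At stake is the reading of the exposure tables: apparent over-delivery of chemotherapy in one measure, and apparent under-delivery of magrolimab in the RDI categories, neither of which took place.

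**Working it through.** The SAP states no dose-intensity result, so there is no figure to reproduce. The check applies its formulas to a fully compliant patient.

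**1. Last cycle, azacitidine and MEC drugs, per actual duration**

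Inputs: planned cycle of 28 days (5.2.2.1); dose given equal to protocol dose D; L = length of the last cycle in days. The SAP gives no dosing days per cycle, so L is an assumption.

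Intensity = (D / L) / (D / 28) × 100 = 2800 / L %.

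| Reading of the closing date | L (days) | Last-cycle intensity |
|---|---|---|
| The drug's own last dose | 3 | 933% |
| | 5 | 560% |
| | 7 | 400% |
| | 9 | 311% |
| Last dose of any study drug | 22 | 127% |
| | 28 | 100% |
| Death date, late death | 60 | 47% |
| | 100 | 28% |

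Whether the day count adds 1 is not stated. Without it, 7 dosing days give 2800/6 = 467%.

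Mean over k cycles, the earlier ones at 100%: (100(k − 1) + 2800/L) / k. With L = 7 this is 400% for k = 1, 250% for k = 2, 175% for k = 4, 150% for k = 6 and 125% for k = 12.

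**2. Measures that the last-cycle rule does not inflate**

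- The per-28-day measure for the same drugs is D / D × 100 = 100%. The two adjacent outputs would disagree for the same compliant cycle.
- Chemotherapy RDI (5.2.2) is total given over total expected, with no cycle length in it.
- Venetoclax per actual duration is days on drug divided by L. With daily dosing and inclusive counting it cannot exceed 100%.

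**3. Magrolimab RDI, literal formula**

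Inputs: the three dose levels in section 1.2, with the assigned dose taken as 30 mg/kg. The number and order of lower doses are not in the SAP, so three patterns are assumed, each followed by 30 mg/kg up to N infusions, all given.

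RDI = (sum of lower doses + 30 × remaining infusions) / (30 × N) × 100.

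| Assumed lower doses (mg/kg) | N = 6 | N = 10 | N = 15 | N = 25 | First N at 90% or more |
|---|---|---|---|---|---|
| 1 | 83.9% | 90.3% | 93.6% | 96.1% | 10 |
| 1, 15 | 75.6% | 85.3% | 90.2% | 94.1% | 15 |
| 1, 1, 15 | 59.4% | 75.7% | 83.8% | 90.3% | 25 |

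Example: pattern 1, 1, 15 with N = 6 gives (17 + 90) / 180 = 59.4%. If the denominator is instead the sum of the doses scheduled at each infusion, RDI is 100% for any pattern and any N.

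**The case against.** The case for leaving the text alone has several parts.

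- **The date can be read differently.** The SAP does not say whose last dosing date is meant; with the last dose of any study drug the excess is 27 percentage points at most over L of 22 to 28. This stands as a limit on size. However, the sentence is framed drug by drug, and section 5.2.1 also uses the last dosing date in a drug-specific definition, so the drug-specific reading is the more natural one. Closing the cycle at a death long after treatment is a strained reading of an on-treatment measure, but the text does not exclude it.
- **Reach.** A reader might infer that the dose-intensity formulas as a whole are wrong, or that the RDI categories would show chemotherapy overdosing. The SAP does not support this: the last-cycle length enters neither chemotherapy RDI nor the per-28-day measures, and section 5.2.2.1 has no categories.
- **Magrolimab.** A reader might conclude that compliant patients will certainly score well under 90%. That needs one reading of the assigned dose, an assumed priming pattern and few infusions. The opening definition in section 5.2.2 supports a dose-by-dose denominator that gives 100%. What stands is a conflict between two definitions, not a certain wrong result.
- **Cohort 2.** One might suppose that most of these patients have a single cycle and so bear the largest effect. The SAP does not say so: section 1.2 allows up to 12 months of treatment, and the window for treatment failure in section 6.2.1 runs to before the third cycle.
- **Importance.** Section 5.2 plans no formal testing of exposure, and tolerability is also described through dose modifications, delays and missed doses (5.2.1) and through adverse events leading to discontinuation, interruption or reduction (7.1.6.1). This stands.

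**Conclusion.** The concern holds in a limited form.

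The last-cycle rule is not fully specified. On its most natural reading, it inflates one measure for four drugs: intensity per actual cycle duration for azacitidine, mitoxantrone, etoposide and cytarabine. For a fully compliant patient the last cycle reads 2800/L %, which is 933% to 311% for an assumed L of 3 to 9 days and at least 200% for any L up to 14. The patient's mean moves towards 100% as cycles accumulate. The other readings give 127% to 100%, or values well below 100% after a late death.

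The magrolimab denominator is defined in two ways within section 5.2.2. Taken literally, the product rule puts a compliant patient with scheduled lower doses below 100%, and below 90% until about 10 to 25 infusions under the assumed patterns. Those percentages rest on the patterns; the conflict in the text does not.

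Both matters concern descriptive exposure summaries. No efficacy test or endpoint is touched.

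**What to change.** 1. **Section 5.2.2.1.** Give the last cycle the planned 28-day length in the per-actual-duration measure, and do not shorten it at death or at the last dose. Shortening at death would bring the inflation back: full dose with death on Day 10 gives 28/10 = 280%. Dropping the last cycle would remove one-cycle patients from the measure.
2. **Section 5.2.2.** Reconcile the two definitions by stating expected magrolimab as the sum, over scheduled infusions, of the dose scheduled at each under the protocol regimen, including any repriming infusions. This takes no position on what those doses should be.

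Each change restores 100% for full compliance. The cost is two sentences and a small programming change. If the programs already work this way, only the text needs correcting; section 1 provides for documenting changes after SAP finalization in the clinical study report.

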5.3. Demographics and Baseline characteristics

Patient demographic variables (eg, age, sex, race, ethnicity) and baseline characteristics (eg, body weight [in kg], height [in cm], body mass index [BMI; in kg/m²], Body Surface Area [BSA; in m²]) and Eastern Cooperative Oncology Group [ECOG] status at baseline will be summarized by cohort and overall using descriptive statistics for continuous variables and using number and percentage of patients for categorical variables. The ECOG status at baseline is the ECOG status at screening. The summary of demographic data will be provided for the All Enrolled Analysis Set.

A by-patient demographic listing, including the informed consent date, will be provided by cohort and patient ID number in ascending order.

Other baseline characteristics, including but not limited to ECOG performance status will also be listed.

5.4. Medical History

Medical history (i.e. conditions not specific to the disease being studied) will be collected at screening for disease-specific and general conditions. A by-patient listing of medical history will be provided by cohort and patient ID number in ascending order.

AML diagnosis history will be summarized by cohort based on the All Enrolled Analysis Set. Time since AML diagnosis (months) will be calculated by (date of first dosing date of study drug (or enrollment date if patient is not treated with any study drug) – date of diagnosis) / 30.4375. Time since AML relapse diagnosis will be calculated as well, if applicable. Time since diagnosis will be summarized using summary statistics for a continuous variable. No formal statistical testing is planned. A by-patient listing of disease-specific medical history will be provided.

In deriving time since disease diagnosis, partial dates of diagnosis will be imputed as follows:

- If day and month are missing but year is available, then the imputed day and month will be 01 Jan.
- If day is missing but the month and year are available, then the imputed day will be the first day of the month.
- Partial date will not be imputed if the year is missing.

5.5. Prior Anti-Cancer Therapy

Prior anti-cancer therapies that patients received, including prior anti-AML therapy and prior anti-MDS therapy, will be listed separately. The details of prior anti-cancer therapy will be listed by patient ID number in ascending order including, regimen name, regimen start/stop date and best response of the regimen.

5.6. Post Study Treatment Stem Cell Transplant

Number and percentage of patients who received post study treatment stem cell transplant will be summarized.

The details of SCT will be listed by patients ID number in ascending order, including date and type of SCT.

5.7. Prior and Concomitant Radiation therapy

No summary or listing of prior and concomitant radiotherapy will be provided.

5.8. Surgeries and Procedures

No summary or listing of surgeries and procedures will be provided.

5.9. Prior Study Transfusion

Number and percentage of patients who received prior transfusions will be summarized. The number of transfusion received within 4 weeks and 8 weeks prior to the first dose will be summarized for whole blood/RBC and platelet as well.

A by-patient listing of transfusion will be provided by cohort and patient ID number in ascending order.

5.10. Prior and Concomitant Medications

Medications collected at screening and during the study will be coded using the current version of the World Health Organization (WHO) Drug dictionary.

5.10.1. Prior Medications

Prior medications are defined as any medications begun before a subject took the first study drug.

No summary of prior medications will be provided.

For the purposes of analysis, any medication with a start date prior to the first dosing date of study drug will be included in the prior medication regardless of when the stop date is. If a partial start date is entered the medication will be considered prior unless the month and year (if day is missing) or year (if day and month are missing) of the start date are after the first dosing date. Medications with a completely missing start date will be included in the prior medication, unless otherwise specified.

5.10.2. Concomitant Medications

Concomitant medications are defined as medications taken while a patient took study drug.

No summary of concomitant medications will be provided.

For the purposes of analysis, any medications with a start date prior to or on the first dosing date of study drug and continued to be taken after the first dosing date, or started after the first dosing date but prior to or on the last dosing date of study drug will be considered concomitant medications. Medications started and stopped on the same day as the first dosing date or the last dosing date of study drug will also be considered concomitant. Medications with a stop date prior to the date of first dosing date of study drug or a start date after the last dosing date of study drug will be excluded from the concomitant medication summary. If a partial stop date is entered, any medication with the month and year (if day is missing) or year (if day and month are missing) prior to the date of first study drug administration will be excluded from the concomitant

medication summary. If a partial start date is entered, any medication with the month and year (if day is missing) or year (if day and month are missing) after the study drug stop date will be excluded from the concomitant medication summary. Medications with completely missing start and stop dates will be included in the concomitant medication summary, unless otherwise specified.

All prior and concomitant medications (other than per-protocol study drugs) will be provided in a by-patient listing sorted by cohort, patient ID number and administration date in chronological order.

5.11. Post Treatment Anti-cancer Therapy

Post treatment anti-cancer therapies will not be summarized. A by-patient listing will be sorted by cohort, patient ID number and administration date in chronological order.

6. EFFICACY ANALYSES

6.1. Primary Efficacy Endpoints

6.1.1. Definition of the Primary Efficacy Endpoints

The primary endpoints are as follows:

• CR Rate (Cohorts 1 and 2): The CR rate is defined as the proportion of patients who achieve CR (CR_{MRD}- or complete remission with positive or unknown MRD [CR_{MRD+/unk}]) as determined by the investigator based on prespecified criteria (Appendix 2) while on study prior to initiation of any new anti-AML therapy (including SCT).

6.1.2. Statistical Hypothesis for the Primary Efficacy Endpoint

The primary efficacy hypothesis for Cohort 2 to be tested is:

 H_0 : CR rate $\leq 19\%$

 H_1 : CR rate > 19%

6.1.3. Analysis of the Primary Efficacy Endpoint

The analyses of primary efficacy endpoint will be based on the FAS.

The point estimates of the CR rate and the corresponding 2-sided exact 95% CIs based on the Clopper-Pearson method will be provided for Cohorts 1 and 2. The CR data will also be tested against the historical control rates 19% (Cohort 2) at 1-sided alpha of 0.1 significance level using 1-group Chi-square test.

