1.3. Sample Size and Power

Sample size calculations for each of the Phase 2 cohorts are as follows:

- For Cohort 1, a sample size of 46 (40 patients in Phase 2 Cohort 1 together with 6 patients in Safety Run-in Cohort 1) provides an 83.6% power for a 1-group Chi-square test at 1-sided alpha of 0.1 level to detect a CR rate of ≥ 53% for the combination compared with a historical control CR rate of 36.7% {DiNardo 2020}.
- For Cohort 2, a sample size of 36 (30 patients in Phase 2 Cohort 2 together with 6 patients in Safety Run-in Cohort 2) provides a 83.1% power for a 1-group Chi-square test at 1-sided alpha of 0.1 level to detect a CR rate of ≥ 35% for the combination compared with a historical control CR rate of 19% {Greenberg 2004}.
- For Cohort 3, a sample size of 46 (40 patients in Phase 2 Cohort 3 together with 6 patients in Safety Run-in Cohort 3) provides a 78.4% power for a 1-group Chi-square test at 1-sided alpha of 0.1 level to detect an MRD negative CR rate of ≥ 33% for the combination compared with a historical control MRD negative CR rate of 20% {Roboz 2020}.

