Appendix Table 1. List of Estimands and Estimators of Main Analyses

Treatments	Variable (Endpoint)	Intercurrent Events & Strategies	Population Level Summary	Estimators
magrolimab + venetoclax + azacitidine, magrolimab + MEC	OS	 Discontinuation of treatment: treatment policy SCT, New anti-cancer therapy: treatment policy 	Kaplan-Meier estimates (medians, Q1, and Q3 of OS distribution, and the proportion of patients who are event free at Weeks 24, 48, and 96 from the first dosing date)	Main Estimator: median OS and 95% CI for each cohort.
magrolimab + venetoclax + azacitidine, magrolimab + MEC	EFS	 Discontinuation of treatment: treatment policy Death, Treatment failure: composite SCT, New anti-cancer therapy: treatment policy 	Kaplan-Meier estimates (medians, Q1, and Q3 of EFS distribution, and the proportion of patients who are event free at Weeks 12, 24, and 48 from the first dosing date)	Main Estimator: median EFS and 95% CI for each cohort.
magrolimab + venetoclax + azacitidine, magrolimab + MEC	CR rate / CR _{MRD} - rate / rate of CR+CRi / rate of CR+CRh/ ORR	 Discontinuation of treatment: treatment policy SCT, New anti-cancer therapy: while-on-treatment Loss to follow-up: while-on-treatment 	Point estimates of the rate and the corresponding 2-sided exact 95% CIs	Main Estimator: Estimate rate and CIs based on the Clopper-Pearson method for each cohort; Test rate against the historical control rate using 1-group Chi-square test for each cohort separately.
magrolimab + venetoclax + azacitidine, magrolimab + MEC	RBC/platelet transfusion independence	 Discontinuation of treatment: while-on-treatment Dose reduction or temporary delay: treatment policy Loss to follow-up: while-on-treatment 	Point estimates of the rate and the corresponding 2-sided exact 95% CIs	Main Estimator: Estimate rate and CIs based on the Clopper-Pearson method for each cohort.

Appendix 2. Disease Response Criteria Based on European Leukemia Net (ELN) and International Working Group (IWG) Criteria

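### At the planned N=36, the Cohort 2 Chi-square test of CR rate has an exact type I error of 13.1%, above its stated 1-sided 0.1 level

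*SAP*

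**What the plan says.** SAP Section 1.3 sizes Cohort 2 at 36 patients, 30 from Phase 2 and 6 from the safety run-in. It says that this "provides a 83.1% power for a 1-group Chi-square test at 1-sided alpha of 0.1 level". The rates behind that figure are a null of 19%, taken from a historical control, and an alternative of 35%. Section 6.4 confirms that run-in and Phase 2 patients are pooled for the primary analysis.

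Section 6.1.2 states a hypothesis for one cohort only: "The primary efficacy hypothesis for Cohort 2 to be tested is" a CR rate of at most 19% against a rate above 19%. Section 6.1.3 sets the population ("The analyses of primary efficacy endpoint will be based on the FAS") and the test: the CR data will be "tested against the historical control rates 19% (Cohort 2) at 1-sided alpha of 0.1 significance level using 1-group Chi-square test". For the same proportion it also says that the "corresponding 2-sided exact 95% CIs based on the Clopper-Pearson method will be provided for Cohorts 1 and 2".

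Section 6.4 drops the Cohort 1 test and all Cohort 3 analyses. Section 6.1.4 plans no sensitivity analysis of the primary endpoint. In the row of Appendix Table 1 that covers CR, CR without MRD, CR+CRi, CR+CRh and ORR, the estimator still includes: "Test rate against the historical control rate using 1-group Chi-square test for each cohort separately".

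The SAP gives no rejection count, no continuity correction, no exact test and no attained type I error. Nor does it give the actual Cohort 2 FAS size.

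**The concern.** With 36 patients and a null rate of 19%, fewer than 7 CRs are expected under the null (36 × 0.19 = 6.84), and the CR count moves in whole patients. A normal-approximation test at this size can have a true error rate well away from its nominal level, in either direction. The SAP quotes the 0.1 level as a property of both the design and the analysis, without checking it against the binomial distribution.

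What is at stake is the reading of a borderline result. This is the one formal test left for the primary endpoint, and no exact analysis is planned that would reveal a discrepancy. At 10 CRs in 36 patients the plan would report significance at 0.1, while the exact p-value is above 0.1. The same section already uses exact inference for the CI, so it handles one proportion by two methods and at two different levels.

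**Working it through.** **Inputs.** N = 36, p0 = 0.19, p1 = 0.35, 1-sided alpha = 0.10 so z = 1.2816 (SAP 1.3, 6.1.2, 6.1.3). CI: 2-sided 95% Clopper-Pearson (6.1.3).

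**1. Reproduce the plan's power.** Null SE = sqrt(0.19 × 0.81 / 36) = 0.06538. Critical proportion = 0.19 + 1.2816 × 0.06538 = 0.2738. Alternative SE = sqrt(0.35 × 0.65 / 36) = 0.07950. Power = Φ[(0.35 − 0.2738) / 0.07950] = Φ(0.959) = 83.1%, as stated. A continuity-corrected version gives 78.3% and a 2-sided 0.10 version 74.5%. So the plan's figure comes from the uncorrected 1-sided form. The same formula also returns the SAP's 83.6% for Cohort 1 and 78.4% for Cohort 3.

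**2. Find the rejection count.** 36 × 0.2738 = 9.86, so the test rejects at 10 or more CRs. At 9 CRs z = 0.918, p = 0.179. At 10 CRs z = (0.2778 − 0.19) / 0.06538 = 1.343, p = 0.090.

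**3. Exact operating characteristics at N = 36.**

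| Rule | P(reject) at 19% | P(reject) at 35% |
|---|---|---|
| Chi-square, 10 or more CRs | 13.1% | 86.2% |
| Exact binomial at 0.1, 11 or more CRs | 6.6% | 76.6% |

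A continuity-corrected Chi-square gives p = 0.129 at 10 CRs and 0.060 at 11, so its rule is the same as the exact one.

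**4. Dependence on the FAS size** (uncorrected Chi-square rule, p0 = 0.19).

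| N | Rejects at | Exact type I error | Exact-test cut-off |
|---|---|---|---|
| 33 | 10 | 8.1% | 10 |
| 34 | 10 | 9.6% | 10 |
| 35 | 10 | 11.3% | 11 |
| 36 | 10 | 13.1% | 11 |
| 37 | 11 | 7.8% | 11 |
| 38 | 11 | 9.2% | 11 |
| 39 | 11 | 10.7% | 12 |
| 40 | 11 | 12.3% | 12 |

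Where the Chi-square rule holds the level, its cut-off equals that of the exact test.

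**5. Test against CI at N = 36.**

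| CRs | Chi-square p | Exact p | 95% CI | 80% CI lower limit |
|---|---|---|---|---|
| 10 | 0.090 | 0.131 | 14.2% to 45.2% | 18.0% |
| 11 | 0.039 | 0.066 | 16.3% to 48.1% | 20.4% |
| 12 | 0.014 | 0.030 | 18.6% to 51.0% | 22.8% |
| 13 | 0.004 | 0.012 | 20.8% to 53.8% | 25.3% |

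At 10, 11 and 12 CRs the Chi-square test rejects while the 95% CI contains 19%. At 11 and 12 the exact test rejects too, so the disagreement there comes only from setting a 10% one-sided test beside an interval with 2.5% in each tail. Only 10 CRs is a conflict between asymptotic and exact inference. At a true rate of 35%, the probability of 10 CRs is 86.15% − 76.57% = 9.6%, and that of 11 or 12 is 76.57% − 50.68% = 25.9%.

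**6. Appendix Table 1 against the main text.** The appendix row applies the historical-control test to every cohort and to five rates. Sections 6.1.2, 6.1.3 and 6.4 confine testing to CR in Cohort 2, Section 6.2.2 gives the secondary rates estimates and CIs only, and the SAP states no historical value for those rates in Cohorts 1 and 2.

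**The case against.** The strongest reply is that the SAP contains no miscalculation. The 83.1% is right for the named method, and the design test and analysis test match. The nominal level of an asymptotic test is commonly understood as approximate. The exact test is conservative here (6.6%), and the mid-p value at 10/36, 0.131 − 0.065/2 = 0.098, agrees with rejection. The SAP describes the study as proof-of-concept, and the disagreement at N=36 is confined to one count. All of this stands. It lowers the severity but does not make 13.1% equal to 10%.

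Four stronger readings are tempting, and the SAP does not support them:

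- A reader might take 13.1% as the error of the analysis as performed. It belongs to N=36. The FAS contains only dosed patients and its Cohort 2 size is not given; at 33, 34, 37 or 38 the level holds and an exact test would change nothing.
- A reader might blame the Chi-square test for every conflict with the 95% CI. At 11 and 12 CRs the cause is the difference in level, which an exact test would leave in place. The SAP does not say that the CI decides the hypothesis.
- A reader might call this the trial's go/no-go test. The SAP attaches no such rule or consequence to rejection.
- A reader might want the test replaced. Section 2.2 says that the primary analysis was conducted with a data cutoff of 1 June 2023, and this SAP version was signed on 31 May 2024. Changing the primary test after that would be post hoc, and worse practice than the defect.

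**Conclusion.** The point holds at the planned size. With N=36, the test in 6.1.3 rejects at 10 or more CRs and has an exact type I error of 13.1% against a stated 10%, an excess of about 3 percentage points. Its exact power at 35% is 86.2%, so neither stated figure is the exact one, although 83.1% is correct as a normal approximation. The practical consequence at N=36 is confined to a result of exactly 10/36.

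This rests on two assumptions. The first is N=36; at nearby sizes the error lies on either side of 10%, so the conclusion must be rechecked at the actual FAS N. The second is that no continuity correction is applied; none is mentioned, and only the uncorrected form reproduces 83.1%. Severity is moderate, given the proof-of-concept setting. The inconsistency in Appendix Table 1 is real but separate, and is not evidence about the error rate.

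**What to change.** - **6.1.3:** keep the prespecified Chi-square test. Add for Cohort 2 CR, labelled supplementary, the 1-sided exact binomial p-value and a 2-sided 80% Clopper-Pearson CI, whose lower limit corresponds to a 1-sided 0.1 exact test. State the attained exact type I error of the Chi-square rule at the actual FAS N. If the exact p-value exceeds 0.1, report the Chi-square result but do not claim success at the 0.1 level.
- **1.3:** leave the design figures, and note that 10% and 83.1% are normal-approximation values. Give the exact values at N=36: 13.1% and 86.2% for the Chi-square rule, 6.6% and 76.6% for the exact binomial rule.
- **Appendix Table 1:** limit the historical-control test to the CR rate in Cohort 2, to agree with 6.1.2, 6.2.2 and 6.4.

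The cost is a few lines of SAP or CSR text and a small amount of programming. The downside is that a borderline result such as 10/36 would be reported less favourably. The additions come after the primary analysis, so they must be identified as such in the CSR.
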